**3.4.3 Exclusion Criteria**

For both rollover subjects from the double-blind trial (331-102-00058) and new subjects, subjects or patients will be excluded from the trial if they meet any of the exclusion criteria, provided in Table 3.4.3-1 at screening (only for new subjects) and baseline.

Table 3.4.3-1 Exclusion Criteria	
Rollover subjects	
1	Female subjects who are pregnant or breastfeeding or who have positive pregnancy test (urine) results at baseline
2	Sexually active male subjects or sexually active female subjects of childbearing potential, who will not agree to practice 2 different methods of birth control or to remain abstinent during the trial and for 30 days after the final IMP administration. For birth control, 2 of the following methods must be used: vasectomy, tubal ligation, vaginal diaphragm, intra-uterine contraceptive device (IUD), oral contraceptives, or condom with spermicide.
3	Subjects who experience a change to the manic state in the antidepressant treatment period (Phase A) of the double-blind trial (331-102-00058)
4	Subjects who are discovered to not meet the inclusion criteria or to fall under any of the exclusion criteria in the double-blind trial (331-102-00058)
5	Subjects who showed marked noncompliance with the IMP treatment in the double-blind trial (331-102-00058) (subjects whose IMP compliance rates are < 65% between prescribed visits)
6	Subjects receiving treatment with antipsychotics and psychostimulants for current major depressive episode (excluding the use of IMP in the double-blind trial [331-102-00058] and use of sulpiride for depression/depressive state or gastric/duodenal ulcer)
7	Subjects receiving treatment with monoamine oxidase inhibitors (MAO inhibitors) within 2 weeks before baseline
8	Subjects using benzodiazepines (excluding ultrashort-acting sleep inducers) within 1 week before baseline
9	Subjects hospitalized for the current major depressive episode after the antidepressant treatment period (Phase A) of the double-blind trial (331-102-00058)
10	Subjects with a history of electroconvulsive therapy
11	Subjects with a diagnosis of any of the following diseases according to DSM-5 
 
a) Neurocognitive disorders
 
b) Schizophrenia spectrum and other psychotic disorders
 
c) Bipolar and related disorders
 
d) Feeding and eating disorders
 
e) Obsessive-compulsive disorder
 
f) Panic disorder
 
g) Posttraumatic stress disorder
 

12	Subjects with a diagnosis of any personality disorders (borderline personality disorder, antisocial personality disorder, paranoid personality disorder, schizoid personality disorder, schizotypal personality disorder, and histrionic personality disorder) according to DSM-5
13	Subjects experiencing hallucinations or delusions, or showing mood-incongruent psychotic features, in the current depressive episode
14	Subjects with a MADRS score of $\geq 5$ for Item 10. Suicide, a Hamilton Rating Scale for Depression (HAM-D) score for suicide (No. 11) of $\geq 3$ , those answering "Yes" to question 4 or 5 of the Columbia Suicide Severity Rating Scale (C-SSRS) at baseline, or those who are, based on current psychiatric symptoms or past medical history, at high risk of suicide during the trial in the opinion of the investigator or subinvestigator
15	Subjects with clinically significant neurological, hepatic, renal, metabolic, hematological, immunological, cardiovascular, pulmonary, or gastrointestinal disorders; subjects can be enrolled if the conditions are mild or well controlled and will not hamper assessment of safety and efficacy.

Table 3.4.3-1 Exclusion Criteria	
16	
Patients meeting any of the following criteria
 
 
• Patients with type 1 diabetes mellitus or patients with type 2 diabetes mellitus being treated with insulin
 
• Patients with type 2 diabetes mellitus who have not been maintained on a stable regimen of anti-diabetic medication(s) or undergone diet/exercise therapy for at least 28 days prior to baseline
 
• Patients meeting either of the following criteria for poor blood glucose control at Week 6 of the double-blind period (Phase B) of the double-blind trial (331-102-00058) (assessed based on results from the central laboratory) 
 
a) HbA1c of <math>\geq 7.0\%</math> according to the global standard value [NGSP value]
 
b) Fasting blood glucose level of <math>\geq 126</math> mg/dL or non-fasting blood glucose level of <math>\geq 200</math> mg/dL
 
 
 

17	Subjects with substance abuse or substance dependence, including alcohol and benzodiazepines, based on DSM-5 diagnostic criteria within 180 days prior to informed consent; caffeine and nicotine are not included.
18	Subjects with a complication of hypothyroidism or hyperthyroidism at informed consent (excluding those in a stable condition due to medications for the previous 90 days or longer), or abnormal thyroid stimulating hormone (TSH) and free thyroxine (FT4) levels at Week 6 of the double-blind period (Phase B) of the double-blind trial (331-102-00058) (assessed based on results from the central laboratory)
19	
Subjects meeting any of the following criteria or showing symptoms at baseline
 
 
a) Poorly controlled hypertension (diastolic blood pressure of <math>> 95</math> mmHg)
 
b) Hypotension with symptoms
 
c) Orthostatic hypotension in which blood pressure after 3 minutes of standing is <math>\geq 30</math> mmHg lower for systolic blood pressure or <math>\geq 20</math> mmHg lower for diastolic blood pressure, compared with pressures in the supine position before standing
 

20	Subjects with a complication of ischemic heart diseases, myocardial infarction, or congestive heart failure (irrespective of well or poorly controlled), or subjects with a history of angioplasty, stent placement, or coronary artery bypass
21	Subjects with a history of neuroleptic malignant syndrome or serotonin syndrome
22	Subjects with a history or complication of epilepsy or epileptic seizures, excluding pediatric febrile seizures, post-traumatic seizures, alcohol withdrawal seizures, and other seizures
23	Subjects with a history of hypersensitivity to antidepressants
24	
Subjects with the following clinical laboratory test values or ECG parameters at Week 6 of the double-blind period (Phase B) of the double-blind trial (331-102-00058) (assessed based on results from the central laboratory and central ECG measurement facility)
 
 
a) Platelet count: <math>\leq 75,000 /\text{mm}^3</math>
 
b) Hemoglobin: <math>\leq 9</math> g/dL
 
c) Absolute neutrophil count: <math>\leq 1000 /\text{mm}^3</math>
 
d) Aspartate aminotransferase (AST): <math>> 2</math> times the upper limit of the reference range
 
e) Alanine aminotransferase (ALT): <math>> 2</math> times the upper limit of the reference range
 
f) Creatine phosphokinase (CPK): <math>> 3</math> times the upper limit of the reference range
 
g) Creatinine: <math>\geq 2</math> mg/dL
 
h) QT interval as corrected by Fridericia's formula (QTcF): <math>\geq 450</math> msec
 

25	Subjects with a history or complication of allergy to more than one medication

Table 3.4.3-1 Exclusion Criteria	
26	The following subjects falling under the contraindications in the package insert for brexpiprazole tablet 
 
a) Subjects in a coma
 
b) Subjects under the strong influence of central nervous system depressants including barbiturate analogs/anesthetics
 
c) Subjects receiving adrenaline
 
d) Subjects with a history of hypersensitivity to components of brexpiprazole tablet
 

27	Subjects who otherwise should not participate in the trial in the opinion of the investigator or subinvestigator
New Subjects	
28	Sexually active male subjects who will not agree to practice 2 different methods of birth control or to remain abstinent during the trial and for 30 days after the final IMP administration. For birth control, 2 of the following methods must be used: vasectomy, tubal ligation, vaginal diaphragm, intra-uterine contraceptive device (IUD), oral contraceptives, or condom with spermicide.
29	Patients who have received at least 4 appropriate antidepressant drug treatments for the current major depressive episode but whose response was inadequate to all treatments
30	Patients receiving treatment with antipsychotics and psychostimulants for the current major depressive episode (excluding the use of sulpiride for depression/depressive state or gastric/duodenal ulcer)
31	Patients receiving treatment with MAO inhibitors within 2 weeks before baseline
32	Patients using benzodiazepines (excluding ultrashort-acting sleep inducers) within 1 week before baseline
33	Patients with a treatment history showing that all antidepressants (also including those not used for the current major depressive episode) cannot be tolerated
34	Patients with a history of electroconvulsive therapy
35	Patients with a diagnosis of any of the following diseases according to DSM-5 
 
a) Neurocognitive disorders
 
b) Schizophrenia spectrum and other psychotic disorders
 
c) Bipolar and related disorders
 
d) Feeding and eating disorders
 
e) Obsessive-compulsive disorder
 
f) Panic disorder
 
g) Posttraumatic stress disorder
 

36	Patients with a diagnosis of any personality disorders (borderline personality disorder, antisocial personality disorder, paranoid personality disorder, schizoid personality disorder, schizotypal personality disorder, and histrionic personality disorder) according to DSM-5
37	Patients experiencing hallucinations or delusions, or showing mood-incongruent psychotic features, in the current major depressive episode
38	Patients receiving a new psychotherapy within 6 weeks prior to informed consent
39	Patients who have previously taken brexpiprazole
40	Patients who have participated in other clinical trials within 60 days prior to informed consent
41	Patients answering "Yes" to question 4 or 5 of C-SSRS at screening or baseline, or those who are, based on current psychiatric symptoms or past medical history, at high risk of suicide during the trial in the opinion of the investigator or subinvestigator
42	Patients with clinically significant neurological, hepatic, renal, metabolic, hematological, immunological, cardiovascular, pulmonary, or gastrointestinal disorders; patients can be enrolled if the conditions are mild or well controlled and will not hamper assessment of safety and efficacy.

Table 3.4.3-1 Exclusion Criteria	
43	
Patients meeting any of the following criteria
 
 
• Patients with type 1 diabetes mellitus or patients with type 2 diabetes mellitus being treated with insulin
 
• Patients with type 2 diabetes mellitus who have not been maintained on a stable regimen of anti-diabetic medication(s) or undergone diet/exercise therapy for at least 28 days prior to screening
 
• Patients meeting either of the following criteria for poor blood glucose control at screening (assessed based on results from the central laboratory) 
 
a) HbA1c of <math>\geq 8.0\%</math> according to the global standard value [NGSP value]
 
b) Fasting blood glucose level of <math>\geq 126</math> mg/dL or non-fasting blood glucose level of <math>\geq 200</math> mg/dL
 
 
 

44	Patients with substance abuse or substance dependence, including alcohol and benzodiazepines, based on DSM-5 diagnostic criteria within 180 days prior to informed consent; caffeine and nicotine are not included
45	Patients with a complication of hypothyroidism or hyperthyroidism at informed consent (excluding those in a stable condition due to medications for the previous 90 days or longer since acquisition of informed consent), or abnormal TSH and FT4 levels at screening (assessed based on results from the central laboratory)
46	
Patients meeting any of the following criteria or showing symptoms at screening or baseline
 
 
a) Poorly controlled hypertension (diastolic blood pressure of <math>> 95</math> mmHg)
 
b) Hypotension with symptoms
 
c) Orthostatic hypotension in which blood pressure after 3 minutes of standing is <math>\geq 30</math> mmHg lower for systolic blood pressure or <math>\geq 20</math> mmHg lower for diastolic blood pressure, compared with pressures in the supine position before standing
 

47	Patients with a complication of ischemic heart disease, myocardial infarction, or congestive heart failure (irrespective of well or poorly controlled), or patients with a history of angioplasty, stent placement, or coronary artery bypass
48	Patients with a history of neuroleptic malignant syndrome or serotonin syndrome
49	Patients with a history or complication of epilepsy or epileptic seizures, excluding pediatric febrile seizures, post-traumatic seizures, alcohol withdrawal seizures, and other seizures
50	
Patients with the following clinical laboratory test values or ECG parameters at screening (assessed based on results from the central laboratory and central ECG measurement facility)
 
 
a) Platelet count: <math>\leq 75,000</math> /mm^3
 
b) Hemoglobin: <math>\leq 9</math> g/dL
 
c) Absolute neutrophil count: <math>\leq 1000</math> /mm^3
 
d) AST: <math>> 2</math> times the upper limit of the reference range
 
e) ALT: <math>> 2</math> times the upper limit of the reference range
 
f) CPK: <math>> 3</math> times the upper limit of the reference range
 
g) Creatinine: <math>\geq 2</math> mg/dL
 
h) QTcF: <math>\geq 450</math> msec
 

51	Patients with a history of hypersensitivity to antidepressants
52	Patients with a history or complication of allergy to more than one medication

Table 3.4.3-1 Exclusion Criteria	
53	The following patients falling under the contraindications in the package insert for brexpiprazole tablet 
 
a) Patients in a coma
 
b) Patients under the strong influence of central nervous system depressants including barbiturate analogs/anesthetics
 
c) Patients receiving adrenaline
 
d) Patients with a history of hypersensitivity to components of brexpiprazole tablet
 

54	Patients who otherwise should not participate in the trial in the opinion of the investigator or subinvestigator

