- 28) Sexually active male subjects who will not agree to practice 2 different methods of birth control or to remain abstinent during the trial and for 30 days after the final IMP administration. For birth control, 2 of the following methods must be used: vasectomy, tubal ligation, vaginal diaphragm, intra-uterine contraceptive device (IUD), oral contraceptives, or condom with spermicide.
- 29) Patients who have received at least 4 appropriate antidepressant drug treatments for the current major depressive episode but whose response was inadequate to all treatments
- 30) Patients receiving treatment with antipsychotics and psychostimulants for the current major depressive episode (excluding the use of sulpiride for depression/depressive state or gastric/duodenal ulcer)
- 31) Patients receiving treatment with MAO inhibitors within 2 weeks before baseline
- 32) Patients using benzodiazepines (excluding ultrashort-acting sleep inducers) within 1 week before baseline
- 33) Patients with a treatment history showing that all antidepressants (also including those not used for the current major depressive episode) cannot be tolerated
- 34) Patients with a history of electroconvulsive therapy
- 35) Patients with a diagnosis of any of the following diseases according to DSM-5
- a) Neurocognitive disorders
  - b) Schizophrenia spectrum and other psychotic disorders
  - c) Bipolar and related disorders
  - d) Feeding and eating disorders
  - e) Obsessive-compulsive disorder
  - f) Panic disorder
  - g) Posttraumatic stress disorder

- 36) Patients with a diagnosis of any personality disorders (borderline personality disorder, antisocial personality disorder, paranoid personality disorder, schizoid personality disorder, schizotypal personality disorder, and histrionic personality disorder) according to DSM-5
- 37) Patients experiencing hallucinations or delusions, or showing mood-incongruent psychotic features, in the current major depressive episode
- 38) Patients receiving a new psychotherapy within 6 weeks prior to informed consent
- 39) Patients who have previously taken brexpiprazole
- 40) Patients who have participated in other clinical trials within 60 days prior to informed consent
- 41) Patients answering "Yes" to question 4 or 5 of C-SSRS at screening or baseline, or those who are, based on current psychiatric symptoms or past medical history, at high risk of suicide during the trial in the opinion of the investigator or subinvestigator

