##### **(2) Method**

A trained and qualified investigator or subinvestigator will assess the following 10 symptoms of depression in the subject on a 7-point scale (0 to 6) using the Structured Interview Guide for the MADRS (SIGMA) at specified assessment time points, and record the date, time, and results of assessment in the source documents and the CRF.

1. Apparent sadness
2. Reported sadness
3. Inner tension
4. Reduced sleep
5. Reduced appetite
6. Concentration difficulties
7. lassitude
8. Inability to feel
9. Pessimistic thoughts
10. Suicidal thoughts

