## (2) Method

A trained and qualified investigator or subinvestigator will assess the following 21 symptoms of depression in the subject on a 5-point scale (0 to 4) for Items No. 1, 2, 10 to 14, 16 to 17, and 19, on a 4-point scale (0 to 3) for Items No. 5 and 20, and on a 3-point scale (0 to 2) for Items No. 3, 4, 6 to 9, 15, 18, and 21 using the Structured Interview Guide for the HAM-D (SIGH-D) at specified assessment time points, and calculate the total score for Items No. 1 to 17, and record the date, time, and results of the assessment in the source documents and the CRF.

1. Depressed mood
2. Work and activities
3. Genital symptoms
4. Somatic symptoms, gastrointestinal
5. Loss of weight
6. Early (initial) insomnia
7. Middle insomnia
8. Late (terminal) insomnia
9. Somatic symptoms, general
10. Feelings of guilt
11. Suicide
12. Anxiety psychic
13. Anxiety somatic
14. Hypochondriasis
15. Insight
16. Retardation
17. Agitation
18. Diurnal variation
19. Depersonalization and derealization
20. Paranoid symptoms
21. Obsessional and compulsive symptoms

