### **3.7.4.6 Columbia-Suicide Severity Rating Scale**

#### **(1) Time points**

At screening (new subjects only), baseline, and Weeks 1, 2, 4, 8, 12, 16, 20, 24, 28, 32, 36, 40, 44, 48, and 52 (or discontinuation), and post-treatment observation

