#### **(2) Method**

This scale consists of the "Baseline Version," which assesses the lifetime history of suicide-related events and suicidal ideation, and the "Since Last Visit Version," which focuses on suicidality since the last assessment in the trial. The "Baseline Version" will be used at screening and the "Since Last Visit Version" will be used at subsequent time points for C-SSRS assessment. The date, time, and results of assessment will be recorded in the source documents and the CRF.

The presence of suicidal ideation 1 or 2 will be assessed with “yes” or “no,” and if the answer to 2 is “yes,” suicidal ideation 3 to 5 will be assessed. If the answer to suicidal ideation 1 or 2 is “yes,” the intensity of ideation will also be rated. Intensity of ideation will be rated on a 5-point scale for “frequency” and “duration” and a 6-point scale for “controllability,” “deterrents,” and “reasons for ideation.” The following suicidal behavior will also be assessed with “yes” or “no,” and the total numbers of each suicide attempt will be recorded. If there is an actual attempt, “actual lethality/physical damage” will be rated on a 6-point scale, and if actual lethality/physical damage is 0, “potential lethality” will be rated on a 3-point scale.

- Suicidal ideation: 1. Wish to be dead 2. Non-specific active suicidal thoughts  
3. Active suicidal ideation with any methods (not plan) without intent to act  
4. Active suicidal ideation with some intent to act, without specific plan  
5. Active suicidal ideation with specific plan and intent

- Suicidal behavior: Actual attempt Non-suicidal self-injurious behavior  
Interrupted attempt Aborted attempt Preparatory acts or behavior Suicidal behavior  
Suicide (only for "Since Last Visit Version")

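### Exclusion criterion 41 for new subjects aged 65 or older lacks the MADRS and HAM-D suicide-item limits that exclude rollovers and force withdrawal on treatment

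*Protocol*

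**What the plan says.** Criterion 41 in Protocol 3.4.3 applies to new subjects, all aged 65 or older. It covers "Patients answering 'Yes' to question 4 or 5 of C-SSRS at screening or baseline, or those who are, based on current psychiatric symptoms" or past history, carry a high risk of suicide in the investigator's opinion. The Synopsis has the same criterion ("Patients answering 'Yes' to question 4 or 5 of C-SSRS at screening or baseline"), again without an item score.

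Criterion 14, for rollovers, has the C-SSRS and judgement parts and two numerical limits: a MADRS score of 5 or more "for Item 10. Suicide, a Hamilton Rating Scale for Depression (HAM-D) score for suicide (No. 11) of" 3 or more.

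Protocol 3.8.3.2, 1) d) lists the same two scores, a C-SSRS question 4 or 5 positive, and the investigator's high-risk opinion as grounds on which a subject must be withdrawn. It does not distinguish rollovers from new subjects.

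The rationale in 3.4.3 gives criteria 14 and 41 the same purpose, reducing suicide risk during the trial. It does not explain the difference.

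**The concern.** The entry rule for the elderly cohort is looser than the exit rule. Two of the four conditions that force a subject out on treatment do not keep a new subject from starting.

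Such a subject could receive brexpiprazole for about a week and then have to leave because of a score already on file before the first dose. The discontinuation would be recorded under the adverse-event heading of 3.8.3.2 and enter the by-reason disposition summary in SAP 7.1. If the site kept the subject on treatment instead, SAP 7.6 would count a major deviation for failing to discontinue. In a cohort planned at 30 and recruited to assess safety in the elderly, even one such case is an avoidable loss of exposure.

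**Working it through.** The plan states no figure on this point, so the check is mainly a comparison of texts.

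**Step 1: compare the conditions.**

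| Condition | Criterion 14 (rollover) | Criterion 41 (new) | Withdrawal 1) d) (all) |
|---|---|---|---|
| MADRS item 10 of 5 or more | yes | no | yes |
| HAM-D item 11 of 3 or more | yes | no | yes |
| C-SSRS question 4 or 5 positive | yes, baseline | yes, screening or baseline | yes |
| Investigator's high-risk opinion | yes | yes | yes |

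No other new-subject exclusion (28 to 54) and no new-subject inclusion (5 to 10) names either item score. The table and the Synopsis agree, so a text-extraction fault is unlikely.

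**Step 2: are the scores available at entry?** Yes. Table 3.7-1 and sections 3.7.2.1 and 3.7.2.4 schedule MADRS and HAM-D at baseline for new subjects, and 3.7.1.3 bases their eligibility on screening and baseline results.

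**Step 3: who passes?** A new subject with a qualifying item score, no C-SSRS question 4 or 5 positive at screening or baseline, and no high-risk judgement. The C-SSRS hurdle is a real one. Section 3.7.4.6 schedules the scale "At screening (new subjects only), baseline, and Weeks 1, 2, 4, 8" and onward, and says "The 'Baseline Version' will be used at screening and the 'Since Last Visit Version' will be used at subsequent time points for C-SSRS assessment". The screening version "assesses the lifetime history of suicide-related events and suicidal ideation". Within this trial rollovers have no screening visit, so on C-SSRS alone criterion 41 is the stricter of the two.

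**Step 4: what happens after dosing?**

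- MADRS item 10 is rated again at Week 1. By 3.7.1.6 that is Day 8 ± 2, so Day 6 to Day 10. With one dose daily from Day 1 to the day before the visit, the count is 6 − 1 = 5 to 10 − 1 = 9 doses, or 8 − 1 = 7 at the reference day, all at 1 mg. If the score is still 5 or more, 1) d) requires withdrawal. If it has fallen below 5, this condition does not.
- HAM-D item 11 is next scheduled at Week 24, or at discontinuation if earlier (3.7.2.4). A qualifying HAM-D score alone therefore forces nothing at Week 1.

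**Step 5: scale.** Protocol 7.1 plans 30 new subjects receiving treatment, so one affected subject is 1/30 = 3.3% of that cohort. This is a share per case and not an estimate of how many there will be. The documents give no item anchors or score distributions.

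**The case against.** The strongest reply is that the remaining gap is very narrow. The subject must have no question 4 or 5 positive on the lifetime C-SSRS or at baseline, and must not be thought high risk by the same role that rates both scales: 3.7.2.1 has "A trained and qualified investigator or subinvestigator will assess the following 10 symptoms of depression in the subject", and 3.7.2.4 uses the same rater for the 21 HAM-D items ("A trained and qualified investigator or subinvestigator will assess the following 21 symptoms of depression in the subject"). An investigator who knows 1) d) would probably treat such a score as high risk, and criterion 54 allows exclusion on opinion. That stands as a limit on size. It does not close the gap, because these routes are discretionary while the rollover and withdrawal limits are fixed.

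A second reply is that cohorts may differ by design. HbA1c, for example, is capped at 7.0% for rollovers and 8.0% for new subjects. This too stands: the documents show neither intent nor oversight. But if entry was relaxed on purpose, the exit rule was not relaxed to match.

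A reader might go further and infer that 1) d) applies from enrolment, so that a subject is at once eligible and due for withdrawal. The documents do not support this. The words in 3.8.3.2 about discontinuing at any time belong to the investigator's discretionary power, and the mandatory list follows in a separate sentence. Sections 3.8.3.1 and 3.7.1.5 place withdrawal in the treatment period, and 3.9 classes a consented subject who does not enter that period as a screen failure.

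Nor does the adverse-event heading in 3.8.3.2 show that an unchanged pre-dose score becomes a treatment-emergent event. It is a category of discontinuation reason.

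**Conclusion.** The mismatch is clear on the text: criterion 41 omits two fixed suicide-risk limits that the protocol applies to rollovers at entry and to everyone on treatment. Its consequence is limited. A new subject can be dosed and then have to be withdrawn at Week 1, provided MADRS item 10 stays at 5 or more. A HAM-D item 11 score alone has no such early effect.

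The number affected is unknown and may be zero. The dose count assumes a first dose on Day 1 and a visit inside the permitted window. Monitoring after entry is adequate, since MADRS item 10 and C-SSRS are rated at every scheduled treatment visit. The SAP plans descriptive summaries with no primary or secondary outcome variable, so no inferential result depends on this. The point is minor. Confidence is high on the textual mismatch and lower on whether any subject will meet it.

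**What to change.** In Table 3.4.3-1 and in the Synopsis, extend criterion 41 so that it also excludes new patients who at baseline score 5 or more on MADRS item 10 or 3 or more on HAM-D item 11. Keep the C-SSRS part (screening or baseline) and the high-risk judgement as they are.

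This is one sentence in two places. Both scales are already rated at baseline in new subjects, so no assessment is added. The downside is that a few new patients may be excluded, including some whose score would have fallen below the limit on treatment.
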